2.1 Study rationale and purpose

The two pivotal Phase III clinical trials (COMFORT-I and COMFORT-II) evaluating INC424 are fully enrolled and published ([Verstovsek 2012](#), [Harrison 2012](#)). Results from the COMFORT-I study ([Verstovsek 2012](#)) published in March 2012 showed a decrease in the spleen size. In addition, symptoms associated with the disease such as weight loss, pruritus, and fever were improved with the treatment. Results from the COMFORT II clinical trial also published in March 2012 ([Harrison 2012](#)), similarly demonstrated a prolonged reduction in spleen volume as well as improvement in overall QOL measures and a reduction in symptoms associated with MF. The NDA filing for INC424 with the FDA occurred on August 3rd, 2011, and FDA approval was granted on November 16th 2011.

While regulatory approval and reimbursement approval are sought, there are no means available for patients with PMF, PPV MF, or PET-MF to receive INC424 outside of a clinical trial. Implementation of an Expanded Access Program will provide an access path to INC424 for patients with PMF, PPV MF, and PET-MF, and enable collection of additional safety and efficacy data until approval by the regulatory agencies or until drug reimbursement is obtained at a country level.

2.2 Rationale for dose and regimen selected

Phase I/II trials evaluated a number of different doses and schedules of INC424. The dose that provided the best clinical outcomes coupled with the optimum safety profile was 20 mg orally BID. Among patients with baseline platelet counts from 100,000 to 200,000/ μ L, a lower starting dose of 15 mg orally p.o. BID should be initiated, and in patients with platelet counts of (75,000 – <100,000/ μ L / μ L) a starting dose of 5 mg p.o. BID should be initiated.

A more recent Phase Ib study (EXPAND) evaluating the safety and MTD of INC424 in patients with lower baseline platelet counts (75,000– 99,000/ μ L) was presented at the American Society of Hematology meeting in December 2012. Enrollment to date suggests that INC424 can be safely administered to patients with lower baseline platelet counts and as such patients with platelet counts of 50,000 – 99,000/ μ L are to be enrolled starting at a dose of INC424 of 5 mg p.o BID. A Phase II study evaluating open-label INC424 in patients with lower baseline platelet counts (50,000 – 100,000/ μ L), presented at the American Society of Hematology meeting in December 2012, supports use of a starting dose of 5 mg p.o. BID ([Talpaz 2012](#)).

3 Objectives and endpoints

3.1 Primary objectives

To collect additional safety of INC424 in patients with PMF, PPV MF, or PET-MF who have either received prior treatment with commercially available agents, investigational drug or who have never received treatment.

3.2 Secondary objectives

- To assess the best overall response rate of INC424 in patients with PMF, PPV MF, or PET-MF, as evaluated by the investigator.
- To collect QoL information in patients with PMF, PPV MF, or PET-MF treated with INC424.
- To document MRU in patients with PMF, PPV MF, or PET-MF treated with INC424.

3.3 Study endpoints

3.3.1 Safety

- Safety and tolerability will be collected by monitoring the frequency, duration and severity of all grade AEs by the National Cancer Institute CTCAE v. 3.0, performing physical exams (PE), and evaluating changes in vital signs (VS), ECOG performance status (PS), electrocardiograms (ECGs) and serum chemistry, hematology results.
- Grade 3 and 4 AEs, Serious Adverse Events (SAEs).
- Change in laboratory values from Baseline to End of Treatment (serum chemistry and hematology).
- Changes in weight from Baseline to each assessment point and at end of treatment.
- Cardiac function as assessed by electrocardiograms (ECGs).

- Changes in vital signs.

3.3.2 Efficacy

- Best overall response to treatment as assessed by spleen palpation (calculated as the percentage change in spleen length compared with baseline).
- Change in spleen length from Baseline to end of each visit.
- Change in WBC and platelet count from Baseline will be summarized to end of treatment.
- Shift in fibrosis in the bone marrow from Baseline to worst/best value on study (where bone marrow biopsies are performed - not mandatory).
- Progression free survival (PFS), acute myeloid leukemia free survival (LFS) and overall survival (OS).
- In patients without splenomegaly, patient reported outcomes measure symptoms of the disease.

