 - b. This error was discovered and all affected Health Authorities were informed. This erroneous amendment 01 version was retrieved. Sites were asked not to use this version and informed that an amendment 02 would be prepared to address the above mentioned errors.

IRB/IEC

A copy of this amended protocol will be sent to the Institutional Review Board (IRBs)/Independent Ethics Committee (IECs) and Health Authorities.

The changes described in this amended protocol require IRB/IEC approval prior to implementation. In addition, if the changes herein affect the Informed Consent, sites are required to update and submit for approval a revised Informed Consent that takes into account the changes described in this amended protocol.

[figure not shown]

Oncology clinical study protocol synopsis

[figure not shown]
Investigational drug	INC424 (ruxolitinib)
Protocol no.	CINC424A2401
Study phase	IIIB
Study title	An open-label, multicenter, expanded access study of INC424 for patients with primary myelofibrosis (PMF) or post-polycythemia vera myelofibrosis (PPV MF) or post-essential thrombocythemia myelofibrosis (PET-MF).
Study population	Male or female patients \geq 18 years of age who have been diagnosed with PMF, PPV MF, or post-essential thrombocythemia myelofibrosis (PET-MF) (Appendix I), who meet intermediate-1 criteria and have palpable splenomegaly of at least 5 cm below the costal margin, or who meet intermediate-2 criteria, or who meet high-risk prognostic criteria. Patients are not required to have received prior therapy for MF.
Study objectives	
Primary objective
 
 - To collect additional safety of INC424 in patients with PMF, PPV MF, or PET-MF, who have either received prior treatment with commercially available agents, investigational drug, or never received treatment. 
Secondary objectives
 
 - To assess the best overall response rate of INC424 in patients with PMF, PPV MF, or PET-MF as evaluated by the Investigator. - To collect (QoL) information in patients with PMF, PPV MF, or PET-MF treated with INC424. - To document MRU in patients with PMF, PPV MF, or PET-MF treated with INC424

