Efficacy assessment(s)	
Response to treatment and disease progression will be assessed by PE, specifically assessing changes in spleen length by palpation. Disease assessment will be performed at screening/baseline, month 1, 2 month 3, and every 3 months thereafter; and at discontinuation of study drug.
 
In patients without splenomegaly, efficacy assessments will only be provided by the patient reported outcomes that measures symptoms of the disease.

Special safety assessment(s)	AEs of all grades, Grade 3/4 AEs, SAEs; laboratory assessments (hematology, serum chemistry, coagulation), vital signs (blood pressure, heart rate, respiratory rate, temperature); cardiac assessments.
Patient reported outcomes	The FACT-Lym (version 4) and the FACIT-Fatigue Scale will be used to document patient reported symptoms including physical well-being, social/family well-being, emotional well-being, functional well-being, constitutional symptoms and fatigue.
Medical Resource Utilization	MRU will be collected up to week 48 to document number of hospitalizations, emergency room visits, outpatient office visits general practitioner, specialist, urgent care visits; transfusions; concomitant medications; and splenectomy/splenic irradiation.
Pharmacokinetics	N/A
Biomarker assessments	N/A

Exploratory Biomarker pharmacodynamic studies involving tumor samples	N/A
Optional Biomarker studies on additional or remaining samples	N/A
DMC	Not applicable

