2.2 Subgroup definitions

No sub-group analyses are planned for this study.

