3.4.3 Analysis of secondary endpoints

In this section the term 'percent of change from baseline' at a time T is defined as per following definition:

$$\% \text{ change at time T} = \frac{\text{Week T value} - \text{Baseline value}}{\text{Baseline value}} \times 100$$

At least 50% reduction in spleen length from baseline at any time: The proportion of patients who achieved at least 50% reduction in spleen length at any time will be displayed along with the 95% CI for proportion of reduction.

If a patient is palpable at Baseline and becomes non-palpable at post-baseline, then this post-baseline value will be imputed as 0 (zero).

The proportion of responders (achieving at least 50% reduction in spleen length at any time from baseline) will be estimated for patients whose spleen were palpable at baseline and remained palpable or became non palpable at the post-baseline visit. In addition to the FAS, this analysis will also be done by the PPS.

Time to response is defined as the time between date of start of treatment to the date of first response. Response is defined by the 50% reduction in spleen length from baseline. Summary statistics for those responders will be provided.

Duration of response is defined as the time between date of first response ($\geq 50\%$ reduction in spleen length from baseline) to date of loss of response or death due to MF. Loss of response is defined as going back to baseline level after first time $\geq 50\%$ reduction in spleen length from baseline. In case a patient does not have loss of response or death due to myelofibrosis by the data cutoff date, DOR will be censored at the date of the last adequate assessment of spleen length OR cut-off date whichever occurs first.

Best overall response to treatment as assessed by spleen palpation is defined by the investigator.

Best overall response is defined as the best response observed during the study follow-up period. The proportion of patients in the best overall response category will be summarized.

In addition, best overall response will be evaluated and summarized by the IWG MRT criteria given in Section 3.11.2.

Change of spleen length from Baseline to end of each visit/month of therapy and at end of treatment. The change in spleen length from Baseline to end of each visit/month of therapy and at end of treatment will be described using descriptive statistics and by relevant change categories:

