3.4.4 Analysis of patient reported outcomes

For the analysis of quality of life assessments/patient reported outcomes (PRO), the scoring of the questionnaires will be handled as specified by the instrument developers.

To assess rate of missing data, a table of completion rates for each questionnaire at each scheduled assessment will be created. The table will include number of patients eligible for PRO assessment and number of patients with complete PRO assessment data, completion will be defined by each instruments scoring guidelines.

Change in individual scores/scales from baseline will be summarized descriptively at each visit. For FACT-Lymphoma scores, repeated measures analysis will also be used.

Change in ECOG Performance Status

The ECOG performance score will be summarized descriptively by visit. The summary will include the number and percent of patients at each reported value. A shift table including the number and percent of patients will also be produced by visit of baseline vs. post-baseline scores.

Change in FACT-Lym scores

The FACT-Lym questionnaire consists of a total of 42 questions contributing to 5 subscales (i.e., physical well-being, social/family well-being, emotional well-being, functional well-being and lymphoma subscale) which in turn contribute to three total sum scores, namely

FACT-Lym Trial Outcome Index (TOI), FACT-General (FACT-G) total score and FACT-Lym total score. More details on the questionnaire and derivation of the score can be found in Section 16.1.9.

Data from FACT-Lymphoma scores will be analyzed in the three sum scores and one subscale LymS. Change and percent change from baseline to each scheduled visit when the FACT-Lymphoma scores were collected will be calculated. The scores will be summarized descriptively by visit. The change from baseline score at each time point will be estimated by using repeated measurement analysis for patients with at least one post-baseline scale score. Patients without baseline value will not be considered in the analysis and baseline is the data collected from the last visit prior to or at Day1.

Time on treatment time will be treated as a discrete variable to allow for a nonlinear relationship between PRO scores and time. Time, DIPSS status and baseline score (as a covariate) will be included in the model as fixed effects, while the patient-specific intercept will be included as a random effect.

DIPSS status will be calculated as per the criteria given in section 3.11.3

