3.11 Other topics

3.11.1 Handling of missing data

Patients with missing baseline values where a change from baseline is calculated or when the baseline is used as a covariate will be excluded from the analysis of that variable. Missing values in the QoL will be handled following the instruction of the instruments.

[figure not shown]
3.11.2 Table of Spleen Response and Loss of Response Criteria by IWG MRT criteria

Patients with spleen length at baseline	Response criteria	Loss of response criteria 1
Less than 5 cm	Non evaluable for response	Non evaluable for loss of response
Between 5 and 10 cm	Responder: achieve non palpable spleen	Splenomegaly 5 cm or more
	Stable disease: does not meet criteria for response NOR for disease progression	Meet criteria of progressive disease
	Progressive disease: increase of 100% from baseline	-
More than 10 cm	Responder: reduction of 50%	Loss of the 50% reduction
	Stable disease: does not meet criteria for response NOR for	Meet criteria of progressive disease

[figure not shown]
	disease progression	
	Progressive disease: increase of 50% from baseline	-

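### Patient-reported outcomes are the named efficacy measure for patients without splenomegaly, but neither protocol section 11 nor the SAP plans a separate analysis of them in that group

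*Protocol*

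**What the plan says.** **The endpoint.** Protocol 3.3.2 (Efficacy) lists as its last item: "In patients without splenomegaly, patient reported outcomes measure symptoms of the disease". The synopsis repeats this under its efficacy endpoints. Under efficacy assessments the synopsis adds: "In patients without splenomegaly, efficacy assessments will only be provided by the patient reported outcomes that measures symptoms of the disease". Quality of life for all patients is a separate list, in protocol 3.3.3.

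**Who is in the group.** The synopsis asks intermediate-1 patients for a palpable spleen of at least 5 cm, but also admits patients "or who meet intermediate-2 criteria, or who meet high-risk prognostic criteria" without a spleen condition. SAP 3.1.2 tabulates prior splenectomy and palpable spleen length as baseline disease characteristics.

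**The planned analyses.**
- Protocol 11.6.5 describes the PRO analyses with no split by spleen status. The only grouping in protocol section 11 is by baseline platelet count.
- SAP 3.4.4: "Change in individual scores/scales from baseline will be summarized descriptively at each visit". It adds a repeated-measures model for FACT-Lym, responder proportions and time to first improvement. None of these is restricted or split by spleen status.
- SAP 2.2: "No sub-group analyses are planned for this study".
- SAP 3.4.3: the proportion with at least a 50% spleen reduction "will be estimated for patients whose spleen were palpable at baseline". The summary of spleen-length change has the same restriction.
- SAP section 4 declares one change from the protocol, the transfusion definitions.

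**The concern.** A patient with no palpable spleen, or with no spleen, cannot show a spleen response. The protocol recognises this and gives these patients a different efficacy measure. Because that item sits in the efficacy list, apart from the all-patient quality-of-life endpoints, it has a purpose only if PROs are reported for this group. A pooled PRO table already follows from section 3.3.3.

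If the plan is carried out as written, the report will contain no PRO estimate for patients without splenomegaly. A reader who asks what the study shows about symptoms in them could be given only the all-patient figure. A separate table requested after the data are known would count as post hoc, although the protocol named the endpoint in advance.

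**Working it through.** The plan has no figure of its own to reproduce here: protocol 11.8 states that no sample size or power computation was made. The check is a tracing exercise, followed by an illustration of precision.

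**Step 1. Trace each efficacy endpoint in protocol 3.3.2 to its analysis.**

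| Endpoint | Planned analysis | Patients without splenomegaly |
|---|---|---|
| Spleen response and spleen-length change | SAP 3.4.3 | Left out (must be palpable at baseline), apart from a count of those who stay non-palpable or become palpable |
| White cell and platelet change | SAP 3.4.3, full analysis set | Included, not separated |
| Marrow fibrosis | SAP 3.4.3, listing where a biopsy was done | Included, not separated |
| Progression-free, leukemia-free and overall survival | SAP 3.4.3, Kaplan-Meier, full analysis set | Included, not separated |
| PROs in patients without splenomegaly | SAP 3.4.4, all patients together | Included, not separated |

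PRO outputs specific to the group: none. The last endpoint is the only one in the list defined by membership of this group, and no planned output is restricted to it.

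**Step 2. Look for another route to the estimate.** The SAP 3.4.4 model contains time, DIPSS status, baseline score and a random patient intercept, so no spleen-status effect can be read from it. The responder analysis excludes only patients who already have the best possible baseline score. SAP 2.2 closes off subgroups.

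**Step 3. Is the group large enough to report?** The documents do not give its size. Inputs: 2238 enrolled (protocol 4.1); assumed share 5%, 10% or 20%; assumed responder proportion p = 0.40.

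Formula: half-width = 1.96 × √(p(1 − p)/n), with p(1 − p) = 0.24.

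- 5%: n = 0.05 × 2238 ≈ 112; 1.96 × √(0.24/112) = 9.1 percentage points
- 10%: n = 0.10 × 2238 ≈ 224; 1.96 × √(0.24/224) = 6.4 points
- 20%: n = 0.20 × 2238 ≈ 448; 1.96 × √(0.24/448) = 4.5 points

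These are best cases. Patients without a baseline score or already at the best score drop out of the responder analysis, later visits lose more, and the questionnaires stop at week 48 (protocol Table 7-1).

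**The case against.** The strongest case on the other side is that little is lost. The study is single-arm and descriptive, protocol 11.6.1 calls the efficacy analyses exploratory, and none of the secondary objectives in protocol 3.2 names this group. The patients are in every PRO table and in the full-analysis-set efficacy results, and protocol section 11 lists all analysed data individually. It also warns that some analyses may not be relevant if numbers are too small. All of this stands and limits the consequence. It does not supply the missing estimate.

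Four stronger readings are tempting, and the documents do not support them.

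- *These patients get no efficacy result, or PROs are their only efficacy endpoint.* The word for exclusivity comes from the synopsis. Section 3.3.2 has no such word and lists survival, blood-count and fibrosis endpoints without regard to the spleen.
- *The SAP silently dropped a planned analysis.* Protocol 11.6.5 does not plan it either. The gap opens inside the protocol, between section 3.3.2 and section 11, and the SAP carries it forward.
- *Pooled PROs overstate benefit in this group because spleen-related relief dominates.* Nothing in the documents shows this. FACIT-Fatigue asks about fatigue and function, and FACT-Lym has no item on early satiety or abdominal discomfort. Neither the direction nor the size of any difference can be established.
- *The SAP 3.11.2 row for baseline spleens under 5 cm, marked "Non evaluable for response", identifies the group.* That row also covers spleens that are palpable but shorter than 5 cm, so it is not a definition of no splenomegaly.

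**Conclusion.** The point holds as a missing analysis. The protocol names PROs as the efficacy measure for patients without splenomegaly, and neither protocol section 11 nor SAP 3.4.4 plans to report PROs for them, while SAP 2.2 rules out subgroups. One stated endpoint therefore has no separate estimate. This rests on reading the last item of section 3.3.2 as an endpoint in that group, which its wording and its separation from section 3.3.3 support.

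The size of the loss cannot be fixed from the documents. Under the two assumptions above, the omitted responder proportion could be estimated to within about 9.1 points at 112 patients and 4.5 points at 448, which is useful for description. A smaller group would give less. No bias in the pooled PRO results is claimed.

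**What to change.** 1. In SAP 3.4.4, define the group as full-analysis-set patients whose spleen is non-palpable at baseline, including those with prior splenectomy.
2. For that group, alongside the palpable group, present change from baseline by visit, responder proportion with 95% CI, and time to first improvement, for the three FACT-Lym sum scores, the lymphoma subscale and FACIT-Fatigue. Label these as the section 3.3.2 efficacy endpoint for these patients. SAP 3.4.4 mentions no interval for the responder proportion, so that is a small addition; the rest is already planned for all patients.
3. Amend SAP 2.2 to match.
4. Reconcile the synopsis statement that efficacy comes only from PROs with the full list in section 3.3.2, and align protocol 11.6.5.

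If the sponsor decides that pooled PROs are enough, the alternative is to withdraw the endpoint openly and record it in SAP section 4.

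The cost is a few more descriptive tables. The questionnaires are already collected at baseline and weeks 4, 12, 24 and 48, and baseline spleen length and prior splenectomy are already recorded. The drawback is limited precision if the group is small, which the intervals would show.

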3.3.3 Quality of Life

(See [Table 7-1](#) for assessments)

- Change in ECOG performance status from Baseline to each visit where the variable is measured.
- Changes in Functional Assessment of Cancer Therapy for patients with Lymphoma (FACT-Lym) version 4 from Baseline to each visit where measured ([Appendix VII](#)).
- Change in the Functional Assessment of Chronic Illness Therapy (FACIT) Fatigue Scale from Baseline to each visit where measured (See [Appendix VIII](#)).

3.3.4 Medical resource utilization (MRU)

[figure not shown]
Medical resource utilization (MRU) will be assessed as follows:

- Frequency and duration of hospitalization from Baseline up to week 48 of therapy
- Frequency of emergency room visits from Baseline up to week 48 of therapy.
- Frequency of general practitioner, specialist, and urgent care visits from Baseline up to week 48 of therapy.
- Number of transfusions and transfusion dependency status end of study.
- Splenectomy and use of splenic irradiation.
- Changes in use of concomitant medications for MPN symptom management ([Appendix IX](#)).

4 Study design

4.1 Description of study design

This is a multicenter, single-arm, open-label expanded access study intended to provide additional data on the safety and efficacy of INC424 in patients with PMF, PPV MF, or PET-MF who have either previously received treatment or have not received treatment.

[figure not shown]

All patients will be treated for PMF, PPV MF, or PET-MF in each participating country with oral INC424 at a dose of 5 - 25 mg (dose based on Baseline platelet count) BID until either:

- Disease progression;
- Transplant;
- Unacceptable toxicity;
- Death;
- Discontinuation from the study for any other reason;
- Physician decision;
- Withdrawal of consent;
- Until 24-months after LPFV; or
- Until the drug is commercially available, whichever occurs first.

The FPFV occurred on 16 August 2011 and the recruitment period ended on December 31, 2014. The study enrolled a total of 2238 patients. The last patient last visit is planned for Dec 2016.

Figure 4-1 Study design

* Baseline evaluations should be performed within 7 days of the first dose of INC424, however platelets should be performed within a maximum of 4 days of the first dose of INC424

All patients should be screened for inclusion and exclusion criteria (Section 5.2 and Section 5.3) within 28 days prior to the first dose of INC424. See Section 7.3 for a description of the required screening evaluations. Baseline evaluations should be performed within 7 days of the first dose of INC424, however platelets should be performed within a maximum of 4 days of the first dose of INC424. See Section 7.4 for a description of the baseline evaluations required.

Screening and eligibility: Eligibility assessment may take place up to 28 days before the first dose of INC424 (Day -28 to Day -1). See Section 7.3 for required assessments.

To avoid duplication of laboratory assessments and other examinations during the 28 days before Day 1, it is permissible to use historical results provided the examinations were performed consistent with protocol requirements 7 days prior to date of first dose, however platelets should be performed within a maximum of 4 days of the first dose of INC424.

Rescreening of patients is permissible at the discretion of the investigator i.e., a patient is screened and is found to be ineligible, they may be rescreened at a later date and entered onto the study provided **all** inclusion and **no** exclusion criteria are met. Rescreening should not occur more often than every 7 days.

Treatment period (open): All patients who consent to study participation will start treatment with INC424 upon meeting all study eligibility criteria. The study period commences on Day 1 (day of first dose of study drug) and continues until either:

- a. Disease progression;
- b. Transplant;
- c. Unacceptable toxicity;
- d. Death;
- e. Discontinuation from the study for any other reason;
- f. Physician decision
- g. Withdrawal of consent;
- h. Until 24-months after LPFV; or
- i. Until the drug becomes commercially available, whichever occurs first

[figure not shown]
Should INC424 not be available to patients after the drug is commercialized or 24-months after LPFV, Novartis will have a local transition plan in place to ensure that patients have access to INC424 without delays to treatment. Once the last dose of INC424 open label study drug is taken, or it becomes commercially available in each participating country or 24-months after LPFV, no further AEs/SAEs will be collected after the required Study Completion (see [Section 7.6.3](#)).

End of study / treatment: Day of last dose of open-label INC424.

Follow-up period: 28 days following the last dose of open-label INC424.

